## **Phase 2 Analytic Plan**

Sample size was set at 125 per arm which, with 20% attrition, would enable detection of small to medium effect sizes of  $d = 0.40\text{SD}$  for continuous outcomes and 38% relative risk reduction for binary outcomes with a power of 80% and  $\alpha = .05$ . Baseline comparability of the intervention and control arms was assessed using two sample t-tests and chi-square. Baseline comparability of the full MOW cohort (intervention plus control) and full COM cohort (intervention plus control), baseline comparability of the MOW intervention and MOW control, as well as the COM intervention and COM control were assessed in the same manner. Mixed models were used to account for having repeated measures (pre and post). All analyses were done in SAS 9.4 and were adjusted for child's sex. Models of BMIz and dietary measures were also adjusted for season of data collection (summer vs. school year) as seasonal differences were

seen in the baseline data for these measures and seasonal differences in preschoolers' BMIZ have been reported in the literature (e.g., Lumeng et al., 2015). Additionally, models in the MOW sample adjusted for family structure and models in the COM sample adjusted for income-to-needs ratio, given baseline differences between the control and intervention groups within these cohorts. Analyses were based on the intention to treat principle such that all randomized participants were included in the analysis based on their randomized intervention group. Significance was assessed using a two-sided test at  $\alpha= 0.05$ .

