## **Phase 2 Study Protocol**

Families were enrolled, consented and randomly assigned to the intervention or to usual care control group. Outcome measures were collected both pre- and post-intervention while data on dietary quality were also collected mid-intervention. Most data were collected in the home; however, with the onset of the global COVID-19 pandemic, data collection was moved to an online platform through which participants completed self-reported questionnaires. Because in-person data collection efforts were not possible, measurements of child height/weight and data on mealtime interactions were not collected for participants with data collection points falling after March 2020. Families received written and verbal information about the study and provided written informed consent. Data collectors and interventionists did not interact, and data collectors were blinded. Participants in the intervention condition received two meals per week for 12 weeks and they received a comprehensive set of cookware/dinnerware at the outset of the intervention delivery.

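### The Phase 2 mixed model names no arm effect; the 80% power figure fits a comparison without baseline, and carries over to arm × time only if the pre-post correlation reaches about 0.47–0.50 (with d in single-time SD units)

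*Combined protocol and SAP*

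**What the plan says.** The Phase 2 Analytic Plan sizes the trial in one sentence: "Sample size was set at 125 per arm which, with 20% attrition, would enable detection of small to medium effect sizes of" 0.40 SD for continuous outcomes, and a "38% relative risk reduction for binary outcomes with a power of 80" per cent, two-sided at 0.05. It gives no pre-post correlation and no control risk, and does not say which SD defines d.

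The analysis is also given in one sentence: "Mixed models were used to account for having repeated measures (pre and post"). The child's sex enters every model, and season enters those for BMIz and diet. In addition, "models in the MOW sample adjusted for family structure and models in the COM sample adjusted for income-to-needs ratio". The reason offered for these two cohort-specific covariates is imbalance: they were added "given baseline differences between the control and intervention groups within these cohorts". No model term is identified as the intervention effect, and the baseline value of the outcome is not among the covariates.

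The Phase 2 Study Protocol says families were "randomly assigned to the intervention or to usual care control group", that "data on dietary quality were also collected mid-intervention", and that "measurements of child height/weight and data on mealtime interactions were not collected for participants with data collection points falling after March 2020".

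**The concern.** When pre and post are both outcomes in one mixed model, at least three arm effects are possible: the arm difference at post, arm × time (the difference in change), and the arm difference at post with the two arms sharing one pre mean. They use the baseline differently, so they give different estimates and different precision. The sample-size sentence matches the first. Arm × time is a common choice for such a model, and its power depends on a correlation that the plan does not give.

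Two things are at stake. A null arm × time result on an outcome that correlates weakly from pre to post could be read as carrying 80% power when it carried less. And the covariates added because the arms differed at baseline may do nothing to the effect tested: a covariate that is constant over time and enters only as a main effect cancels from within-family change.

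**Working it through.** **Inputs from the Phase 2 Analytic Plan:** 125 per arm, 20% attrition, d = 0.40, two-sided 0.05, 80% power. **Assumed:** r from 0.2 to 0.7; d in units of the outcome's SD at one time; equal pre and post variances (SD = 1).

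**1. The plan's own figure.** n = 2(1.960 + 0.842)² / 0.40² = 98.1, so 99 per arm; 99 / 0.8 = 123.75, so 124, against 125 stated. With 125 × 0.8 = 100 per arm, SE = √(2/100) = 0.141 and power by noncentral t is 80.4%. The figure reproduces without any use of baseline.

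**2. Power of the other effects at d = 0.40.**

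- Arm × time, 100 completers per arm: SE = √(4(1 − r)/100).
- Arm × time, also using the 25 per arm with pre only: SE = √(2[(1 − r²)/100 + (1 − r)²/125]).
- Post difference with a common pre mean, 100 completers per arm: SE = √(2(1 − r²)/100).

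| r | Arm × time, completers | Arm × time, all pre values | Common pre mean |
|---|---|---|---|
| 0.2 | 60% | 64% | 82% |
| 0.3 | 66% | 69% | 84% |
| 0.4 | 73% | 75% | 87% |
| 0.5 | 80% | 82% | 90% |
| 0.7 | 95% | 96% | 98% |

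Arm × time reaches 80% at r = 0.495 (completers) or 0.467 (all pre values). Above that the plan's figure is conservative. The variance of the common-pre-mean effect relative to arm × time in completers is 2(1 − r²) / 4(1 − r) = (1 + r)/2, which is below 1 for every r below 1. Relative to post alone it is 1 − r², which is never above 1.

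**3. If d is in SDs of change.** The calculation in step 1 then applies to the change score itself: 100 per arm gives 80.4% for arm × time at any r.

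**4. Difference between the estimates.** Arm × time is the post difference minus the pre difference; the baseline-adjusted effect is the post difference minus r times the pre difference. They differ by (1 − r) × the pre difference. One standard error of chance imbalance is √(2/100) = 0.141 SD; at r = 0.3 the gap is 0.7 × 0.141 = 0.10 SD, a quarter of the planned effect.

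**5. Covariates under arm × time.** In one simulated trial (100 per arm with both measurements, covariate prevalence 60% against 40% by arm), the arm × time estimate was 0.09116 without covariates, the same with the covariate and sex as main effects, and 0.03667 with the covariate × time term. Season can differ between a family's visits, so it is outside this point.

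**6. Binary outcomes.** At 100 per arm and 80% power, the detectable relative reduction is 38.2% (unpooled variance) or 38.6% (pooled) at a control risk of 50%, and about 54% at 30%. The 38% therefore implies a control risk of about 50%.

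**7. Loss above 20%.** With an assumed 80 completers per arm, even the common-pre-mean effect has 73% power at r = 0.2 and 75% at r = 0.3.

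**The case against.** The best reply is that nothing has been shown to be wrong. The sample size reproduces. Power is at least 80% for the post difference, for the baseline-adjusted effect at every r, and for arm × time once r reaches about 0.5. A shortfall needs arm × time, single-time SD units and a low r together, and the documents establish none of the three. The Phase 1 Analytic Plan applies Cohen's d to pre-post changes, which lends some support to change-SD units in Phase 2; it concerns another phase, so it does not settle the matter. This objection stands: a reader might infer that the trial was underpowered, and the documents do not support that.

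Three other strong readings also fail. A reader might infer an inflated false-positive rate from free choice between effects; that needs selective reporting, which nothing in the text suggests. A reader might put a ceiling on the cohort sample sizes; the documents give neither the MOW and COM sizes nor their balance by arm. And a reader might conclude that the model excludes the mid-intervention diet measurement; the mention of pre and post may describe outcomes in general, and a mixed model can take a third time, so this is an ambiguity.

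It can also be said that naming the term would be enough. That would close the reporting gap. It would not obtain the precision available from data already held, or remove chance baseline differences from the estimate.

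**Conclusion.** The concern holds as a conditional one. The plan does not name the Phase 2 arm effect, and its power figure belongs to a comparison that makes no use of baseline. If arm × time was tested, with d in single-time SD units and equal variances, 80% power needs r of about 0.47–0.50, and power is about 60–75% at an assumed r of 0.2–0.4. In change-SD units the condition disappears; the unnamed effect remains. Under arm × time, sex, family structure and income-to-needs ratio as main effects leave the estimate unchanged in families with both measurements.

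The 80% figure should not be carried to outcomes with clearly fewer than 100 completers per arm. BMIz and mealtime outcomes may be among these, since their in-person collection stopped after March 2020. Nor should it be carried to the separate MOW and COM models without their numbers. This is a worthwhile and cheap improvement. It is not evidence that the trial or its results are wrong.

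**What to change.** 1. **Name the main effect.** Use the arm difference at post from the mixed model with a common pre mean in both arms, which the stated randomisation justifies. In families with both measurements this is in effect post regressed on arm and pre. Enter the covariates the plan already lists so that they act on the post difference: with a time interaction, or as covariates in the regression for post. For dietary quality, say how the mid-intervention measurement enters and keep post as the main effect.

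2. **Restate the sample size.** Give the SD behind d; say whether 125 per arm is overall or per cohort; say that 38% corresponds to a control risk of about 50%; and limit the 80% to outcomes with about 100 completers per arm. For BMIz, mealtime outcomes and the cohort models, make no power claim unless their numbers support it. Whether the cohort effects are primary or secondary is for the sponsor to state.

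**Cost.** Models are re-run on data already held, at a few degrees of freedom and with no extra participants. If a baseline-adjusted effect was already used, only wording changes. If another effect was reported, keep it, add this one and label it post hoc. The gain over arm × time is about 18–21 points of power at r = 0.2 and 8–10 at r = 0.5, but only about 2 at r = 0.7, so it is small for outcomes that are stable from pre to post.
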